# 4. Inclusion/Exclusion Criteria:

Inclusion Criteria	Exclusion Criteria
English speaking	Non-English speaking
At least 18 years old	Less than 18 years old
Must be a patient of the UAB Dental School	Smokers/tobacco users (>10 cigarettes/day)
Able to read and understand informed consent document.	Patients with systemic pathologies or conditions contraindicating oral surgical procedures or adversely affecting wound healing.
Need for implants to replace missing tooth or teeth in at least one quadrant of the mouth.	Patients with significant medical conditions or habits expected to interfere with bony healing.
Insufficient alveolar ridge width for endosseous implant placement defined as 5mm or less as determined by bone sounding and cone beam computed tomography (CBCT) scan.	Patient is a poor compliance risk (i.e., poor oral hygiene, history of alcohol or drug abuse).
Patient and/or guardian is willing and able to comply with the preoperative and postoperative diagnostic and clinical evaluations required.	Bone dehiscence of >4mm following tooth extraction or Vertical loss of bone at edentulous ridge.
Patient not pregnant or not breastfeeding.	Patient pregnant or breastfeeding.

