#### 2. Background

Dental rehabilitation of partially or totally edentulous patients with oral implants has become a routine treatment modality in the last decades, with reliable long-term results. Early loss of the teeth due to trauma or periodontitis often leads to deformities in these resulting edentulous ridges. Studies have demonstrated that bone resorption will occur secondary to tooth extraction. This tends to occur over a 12-month period, most notably in the first 4 months following extraction.

When a tooth or a group of teeth has been missing for a long time, the patient may present with a ridge that is deficient in thickness and/or height and inadequate for dental implant placement. In these cases, ridge augmentation using guided bone regeneration (GBR) is routinely used to regain the lost bone.

The concept of GBR is based upon the use of a barrier membrane to exclude rapidly growing soft tissue cells from a bony defect and, more importantly, to maintain a space for the slower process of bone formation. Bone grafts or bone substitutes are commonly used in GBR procedures to provide support for the barrier membrane, for additional space maintenance, and/or for their bone healing properties.

An important factor is flap closure during bone augmentation. The key to achieving wound closure is not only the clinician's ability to obtain tension-free release flap but also good soft tissue quality and quantity. In an attempt to achieve wound closure and hence graft stability, the buccal mucosa is often broadly released, and this often results in a severe apical translocation of the mucogingival line, loss of vestibule, and keratinized mucosa (KM). When the vestibule becomes shallow, it often leads to an esthetic challenge as well as a phonetics problem. Moreover, research has shown that areas with minimal KM often have a higher peri-implant plaque accumulation, inflammation, and attachment loss.

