Various surgical techniques have been used to obtain adequate amounts of keratinized tissue around dental implants, including the gingival autograft, apically positioned flap (APF), coronally positioned palatal sliding flap, and acellular dermal matrix graft (ADM). Performing a free gingival graft (FGG) prior to im- plant surgery has been suggested when there is minimal keratinized tissue over the edentulous ridge and APF and FGG can be combined in shallow vestibules with minimal keratinized tissue. A recent systematic review demonstrated that the combination of apically positioned flap and free gingival graft (FGG) is the most successful approach to increase the width of keratinized tissue and deepen the vestibule. However, when comparing the use of epithelialized gingival grafts with free connective tissue grafts, their ability to promote keratinized tissue is similar.

These procedures are usually performed before implant placement or during the exposure of submerged implants, which can extend the healing period and result in patients suffering from pain and discomfort through several surgical stages. In addition, these can be time-consuming procedures in cases that already have good primary implant stability and do not need hard-tissue augmentation.

To our knowledge, the influence of soft tissue augmentation at the time of ridge augmentation procedure has not been tested in socket grafting (ridge preservation) and ridge augmentation (deficient healed site) defects. This study aims at evaluating the effects of soft tissue augmentation using CTG or ADM on the clinical (amount) and histologic (% vital bone) outcomes at time of lateral ridge augmentation.

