### 3. Study Population, Protocol Procedure, and Method:

Approximately 60 adults determined to need ridge augmentation graft of any ethnicity or gender with established UAB School of Dentistry Records may be enrolled in the study.

Participants must be at least 18 years old with demonstrated ability to understand and consent to the proposed study procedure. Decisionally-impaired adults and/or minors who cannot consent for themselves will not be enrolled. Women who report a current pregnancy or patients who are not systemically healthy enough to receive out-patient elective dental care at the time of enrollment will be excluded.

All attending faculty and residents in the UAB Department of Periodontology will be notified of this study. Patients seeking dental implant therapy routinely present to the Periodontal clinic to have a consultation regarding ridge augmentation. Upon completion of the exam by the periodontal resident faculty members will confirm the appropriate treatment plan (bone grafting). If the patient is considered potentially eligible the PI will be asked to explain the study procedures and confirm eligibility based on the clinical and radiographic findings (inclusion criteria). Candidates will be provided an unsigned copy of the consent form to take with them. Participants will be given a minimum of 24 hours to decide upon participation. Upon agreement for study entry patients will be scheduled by the research team for a screening visit, signing of the Informed Consent document and scheduling of the surgical procedure.

**Screening/baseline visit:** Upon enrollment into the study the patient's medical history and electronic records will be reviewed. Clinical examiners will conduct clinical and radiographic review/exams, the data will be used to determine eligibility according to the inclusion criteria. Study visits and objectives will be explained to all participants. IRB approved written informed consent will be obtained from all the participants.

**Surgical visit (Visit 1):** Patients will be randomized like the flip of a coin to one of the three groups listed on the day of surgery. Randomly generated treatment groups will be printed on note cards and placed in sealed envelopes. Envelope will be opened during the visit.

Group 1: Connective tissue graft (CTG) at time of lateral ridge augmentation, or

Group 2: Acellular Dermal Matrix (ADM) at time of lateral ridge augmentation.

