Group 3: Control group (no soft tissue augmentation at time of lateral augmentation)

During bone augmentation procedure, just before suturing the flaps that were reflected, a CTG (Harvested from the patient's palate) or ADM (donor tissue that is FDA approved) will be sutured to the membrane that covered the bone graft.

**Visit 2:** The sutures will be removed after two weeks. Surgical sites (CTG, ADM or Control group) will be evaluated for healing status and postoperative instructions on resuming oral hygiene measures will be instructed to patients. Review medical history and assess for adverse events experience.

**Visit 3:** Six months post-ridge augmentation, For the research purposes a soft tissue biopsy will be taken at the center of the augmented site after elevating the flap using a 2 mm tissue punch. It is noteworthy that this soft tissue specimen would have been typically drilled away (automatically discarded in the suction system) with the initial implant site preparation drill if a biopsy were not planned (regular clinical setting). Hence, the biopsy procedure will not affect in any negative way the likelihood of implant placement. One Soft tissue biopsy per every participant in each group will be harvested from the site that was augmented and each tissue sample will be labelled a unique set of numbers and/or letters.

The soft tissue biopsy will be harvested and fixed in special solution overnight at 4°C. Fixed tissues will be dehydrated through an ethanol gradient, cleared in xylene, and embedded in paraffin. Embedded Tissues will be sagittal sectioned at 7mm thickness and mounted on Superfrost Plus slides (Fisher Scientific, Hampton, NH, USA). Serial sections of biopsy containing epithelia and connective tissue will then be cleared in xylene, rehydrated, and stained with hematoxylin and eosin (H&E) according to

standard protocol. The samples will be store to the laboratory located in the Institute of Oral Health Research at UAB School of Dentistry for the analysis of the tissue samples.

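### Eligibility does not rule out recent extraction sites, and neither allocation nor analysis takes account of time since extraction, so a mix of site types could cost precision

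*Combined protocol and SAP*

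**What the plan says.** All references are to the combined protocol and SAP.

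- **Eligibility (section 4).** Patients qualify by "Need for implants to replace missing tooth or teeth in at least one quadrant of the mouth" and by "Insufficient alveolar ridge width for endosseous implant placement defined as 5mm or less as determined by bone sounding" and CBCT. The one criterion that mentions extraction is the exclusion "Bone dehiscence of >4mm following tooth extraction or Vertical loss of bone at edentulous ridge". It sets one limit for sites after an extraction and another for edentulous ridges. No criterion gives a minimum or maximum time since extraction.
- **Rationale (section 2).** Resorption follows extraction, and "This tends to occur over a 12-month period, most notably in the first 4 months following extraction". The usual setting for ridge augmentation is described thus: "When a tooth or a group of teeth has been missing for a long time, the patient may present with a ridge that is deficient". The untested question is said to cover two settings: soft tissue augmentation "has not been tested in socket grafting (ridge preservation) and ridge augmentation (deficient healed site) defects".
- **Timing (section 3, Visit 3).** "Six months post-ridge augmentation, For the research purposes a soft tissue biopsy will be taken".
- **Allocation (section 3, Visit 1).** Three groups, coin-flip wording, and "Randomly generated treatment groups will be printed on note cards and placed in sealed envelopes". No stratification or blocking is stated.
- **Analysis (section 7).** The only test named is a two-sided, unequal-variance, two-sample t-test. No adjustment is mentioned.
- **What is measured.** Core objective 2 (section 1) is the effect on bone regeneration. The four listed outcomes are soft tissue histology, keratinised width, soft tissue thickness, and soft tissue volume from superimposed scans.

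**The concern.** On the protocol's own account, a ridge that has recently lost a tooth is still changing and a long-healed ridge is not. A site grafted soon after extraction could pass through its most active period inside the six months before Visit 3. A healed site would not. If both types are enrolled, part of the spread in some outcomes reflects the age of the site and not the graft.

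Two things follow. The within-arm variance grows, which lowers power. And with about 20 patients per arm and no stratification, one arm may by chance hold noticeably more recent sites than another, which moves the observed difference in that one trial. If time since extraction is not recorded, the sponsor can neither show that the arms were comparable nor adjust for a difference later.

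**Working it through.** **Inputs from the protocol.** Enrolment is 60 in three groups, so 60/3 = 20 per arm if the groups are equal. Section 7 also gives 22 per group, power 0.90 and two-sided alpha 0.05, but no effect size and no SD.

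**Assumptions, since the protocol gives no figures.** p is the share of recent extraction sites, taken as 10%, 20%, 30% and 50%. D is the difference in outcome between site types in within-type SDs, taken as 0.5 and 1.

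**Step 1: the plan's own figure.** The 22 per group cannot be reproduced without an effect size. Solving the t-test power function backwards, 22 per group at 0.90 power corresponds to a standardised difference of about 1.00. At that difference, 20 per arm gives power 0.87.

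**Step 2: chance imbalance.** The number of recent sites in each arm is treated as an independent Binomial(20, p). A difference of 4 patients is 4/20 = 20 percentage points.

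| Share p | Two given arms differ by 4 or more | Largest and smallest of three arms differ by 4 or more |
|---|---|---|
| 10% | 0.06 | 0.14 |
| 20% | 0.16 | 0.34 |
| 30% | 0.23 | 0.45 |
| 50% | 0.27 | 0.51 |

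**Step 3: what a 20-point imbalance does.** Shift in the unadjusted arm difference = 0.20 × D. This is 0.1 SD at D = 0.5 and 0.2 SD at D = 1. For scale, the standard error of an arm difference at 20 per arm is √(2/20) = 0.32 SD.

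**Step 4: variance.** Mixture variance relative to a single site type = 1 + p(1 − p)D².

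- p = 0.5, D = 0.5: 1 + 0.25 × 0.25 = 1.06, a rise of 6%.
- p = 0.5, D = 1: 1 + 0.25 × 1 = 1.25, a rise of 25%.
- p = 0.1, D = 1: 1 + 0.09 × 1 = 1.09, a rise of 9%.

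**Step 5: power.** Suppose the back-solved difference of 1.00 SD refers to a single site type. Dividing it by the square root of the variance ratio for a 50:50 mix gives the unadjusted power:

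| Per arm | One site type | D = 0.5 | D = 1 |
|---|---|---|---|
| 22 | 0.90 | 0.88 | 0.83 |
| 20 | 0.87 | 0.85 | 0.79 |

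**The case against.** The strongest reply is that recent sites may not be enrolled at all. The title and all three arms speak of lateral ridge augmentation. Section 2 attaches the words for a deficient healed site to ridge augmentation and keeps socket grafting separate, and its remark on socket grafting describes a gap in the literature, not the enrolled population. The extraction wording in section 4 says nothing about how recent the extraction is. This stands as a limit: enrolment of recent sites is an inference. It does not settle the matter, because a dehiscence limit after extraction has little purpose if no such site can enter, and nothing in section 4 shuts them out.

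The mechanism is also an extrapolation. Section 2 describes resorption after extraction, whereas every arm here, control included, receives a bone graft. The protocol says nothing on how grafted recent and grafted healed sites differ at six months. None of the four listed outcomes measures bone dimensions, and the volumetric outcome is defined on soft tissue. A surface scan may also pick up change in the underlying bone, so a link to volume is plausible but not quantified. It is weaker for keratinised width and histology.

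A reader might infer that a chance excess of recent sites would pass for a graft effect and so bias the trial. The documents do not support that. Allocation is random, so imbalance of this kind is already covered by the test's type I error rate. What remains is lost precision and a single estimate that is harder to interpret.

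**Conclusion.** The point holds as a gap in definition and a risk to precision. Section 4 leaves recent extraction sites admissible, section 2 gives a reason to expect site age to matter, and sections 3 and 7 neither record it, stratify by it nor adjust for it.

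The size depends on two quantities that the protocol does not give. At a 10% share of recent sites the matter is minor. At a 30% to 50% share, a 20-point gap between two given arms arises in about a quarter of trials. The resulting shift of 0.1 to 0.2 SD stays below one standard error. The cost in power for a 50:50 mix runs from about 2 points (site effect 0.5 SD) to 7 or 8 points (1 SD). If only healed sites are treated, the concern falls away. It bears most on core objective 2 and the scan-based volume outcome.

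**What to change.** 1. State in section 4 whether recent extraction sites are eligible. Which sites to admit is for the investigator. The statistical need is that the text be explicit.
2. Add time since extraction to the screening form. Records and radiographs are already reviewed at that visit.
3. If both types are eligible, define the site classes in advance and classify each site before the envelope is opened. Prepare one envelope series per class, **with permuted blocks within each series**. Separate series without blocks would leave the imbalance in place. With blocks that hold each arm once or twice, the arms within a class can differ by at most 1 or 2 patients.
4. Replace the unadjusted two-sample t-test, which cannot carry a covariate, with a linear model for the continuous outcomes that includes arm and site class. Time since extraction as a covariate is an alternative. It avoids treating sites just past a cut as fully healed, when section 2 lets resorption run to 12 months.

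The cost is one screening field, slightly more envelope handling, a rewritten analysis paragraph and one degree of freedom. No treatment or visit changes. If only healed sites enrol, one envelope series stays unused and almost nothing is lost.

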### 5. Benefits

Following a conventional lateral ridge augmentation, a displacement of the alveolar mucosa will take place because of the periosteal release that is part of the ridge augmentation procedure to achieve passive closure. Usually, this soft tissue defect that is created on the ridge where it will receive implants is corrected by a free gingival graft before, or at the time or after implant placement in order to create attached tissue adequate for future implant success. Benefits of this project is to monitor the expected benefits of using soft tissue grafting at the time of lateral ridge augmentation in creating a thicker tissue and possible attached soft tissue on the sites that will receive implants after the bone graft healing potentially leading to higher implant survival. This will decrease the number of surgeries and patient morbidity as the two procedures are going to be performed at the same visit.

#### 6. Risks

Regarding procedural risks, due to each subject's physical and dental conditions being unique, the success of soft tissue grafting cannot be guaranteed. Some discomfort after treatment can be expected.

This may include pain, bleeding, inflammation, and soreness. These discomforts can be expected to go away within approximately 48 hours. The treatment site could become infected. If an infection occurs, the study dentist will treat the area.

Risks in group 1, post-operative discomfort may be expected with harvesting of the CTG although there is a considerable variability in patient reported discomfort after having received the same treatment with either group.

Risks associated with use acellular dermal matrix (group 2) include a low, theoretical possibility of viral or prion contamination of the materials. No such contamination has ever been reported and ADM has been used in many medical and dental applications. ADM is processed from cadaveric donor skin and all donors are tested for nondetectable levels of HIV and HepC. Furthermore, it is processed using proprietary methods to removal all cells and cellular components (and this is histologically verified for each processing batch) to allow the collagenous and extracellular framework to remain without the cells which may produce antigenicity.

Regarding the randomization risk, patients will be assigned to a group by chance, which may prove to be less effective than the other. There is a chance that one procedure may have a risk of increased post-operative discomfort, although there is considerable variability in patient reported discomfort after having received the same treatment with either group.

There are no additional risks associated with the soft tissue biopsy in addition to those associated with the routine implant site preparation itself. The biopsy trephine will simply replace the initial implant drill, as it will have the same dimensions.

Other risks associated with this protocol involve potential loss of confidentiality. Precautions will be taken to ensure that patient confidentiality is maintained. All records will be assigned identifying alphanumeric codes and the list linking identifying PHI to patient data will be kept on a password protected computer and destroyed immediately after statistical analysis is completed. All consent documents will be assigned non-identifying, alpha-numeric codes and the list linking personal information and patient data will be kept on a password protected computer and destroyed immediately after data analysis have been completed.

There may be other risks that are unknown.

#### 7. Data Analysis/Outcome measures

The null hypothesis is CTG and ADM materials will have the same soft tissue thickness and possible attached tissue (as demonstrated by histology) at time of implant placement. To reject the null hypothesis of equal means with a significance level (alpha) of 0.05 using a two-sided two-sample unequal-variance t-test, 22 patients in each group (total of 66) will reach 0.90 statistical power. Accounting for a 6-patient loss-to-follow up, 60 patients will be enrolled in the study.

Outcomes will be measured by an evaluation of the following:

- 1) the quality of soft tissue regenerated with the use of the two available soft tissue grafts via histological analysis (attachment to bone and keratinization)
- 2) Keratinized tissue width (in mm) measured clinically with a periodontal probe from the implant collar to the mucogingival junction.
- 3) Vertical thickness of soft tissue (in mm) measured clinically with a periodontal probe around the implant collar from soft tissue surface to bone contact.

4) Volumetric change of soft tissue dimensions around the implant collar evaluated by superimposition of pre- and post-grafting digital intra-oral scans

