# A randomized controlled Trial to Compare the Histomorphometric and Clinical Outcomes of Soft Tissue Augmentation at the Time of Lateral Ridge Augmentation Procedures.

### Study Protocol

### 1. Objectives/Specific Aims:

The purpose of this investigator-initiated study is to evaluate the effect of soft tissue autogenous vs allogenic grafts on the soft tissue quantity and quality at the time of Guided Bone Regeneration (GBR) in preparation for endosseous implant placement.

Autogenous Connective Tissue Grafting (CTG) and Acellular Dermal Matrix (ADM) soft tissue grafts are mainly used to alter the quality and quantity of soft tissue.

a) Core objectives of this study are to:

1) To evaluate the quality of soft tissue regenerated with the use of the two available soft tissue grafts via histological analysis.

2) To evaluate whether CTG or ADM influences the outcomes of Guided Bone Regeneration (GBR) procedures.

3) To quantify the soft tissue augmentation achieved by the two available soft tissue grafts by direct clinical measurements after the healing

b) Outcomes will be measured by an evaluation of the following:

- 1) The quality of soft tissue regenerated with the use of the two available soft tissue graft via histological analysis (attachment to bone and keratinization)
- 2) Keratinized tissue width (in mm) measured clinically with a periodontal probe from the implant collar to the mucogingival junction.
- 3) Vertical thickness of soft tissue (in mm) measured clinically with periodontal probe around the implant collar from soft tissue surface to bone contact.
- 4) Volumetric change of soft tissue dimensions around the implant collar evaluated by superimposition of pre- and post-grafting digital intra-oral scan.

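### One null hypothesis covers both soft tissue thickness and histological attachment, so the stated alpha of 0.05 and power of 0.90 cannot both describe the joint test, and 0.90 is not established for histology

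*Combined protocol and SAP*

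**What the plan says.** Section 7 (Data Analysis/Outcome measures) gives the only hypothesis in the document: "The null hypothesis is CTG and ADM materials will have the same soft tissue thickness and possible attached tissue (as demonstrated by histology"), assessed at implant placement. The next sentence treats this as a comparison of means: "To reject the null hypothesis of equal means with a significance level (alpha) of 0.05 using a two-sided two-sample unequal-variance t-test". The power claim follows directly: "22 patients in each group (total of 66) will reach 0.90 statistical power". Enrolment is then set at 60, with 6 losses allowed for.

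The two parts of the null are described differently. Thickness has a unit: "Vertical thickness of soft tissue (in mm) measured clinically with a periodontal probe around the implant collar". Histology is described, in Section 1 and again in Section 7, only as tissue quality "via histological analysis (attachment to bone and keratinization"). No score, unit, grading or expected rate is given. Section 3 adds that there is one H&E-stained punch biopsy per participant, taken six months after augmentation.

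No other test, alpha or power figure appears anywhere. There is no rule for combining the two parts, and no difference or SD for either.

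**The concern.** An alpha and a power belong to a defined test with a defined rejection rule. Here two different quantities share one null and one test of means, and the rule is missing. It could be that either part is enough to reject, or that both are needed. The two readings have different type I error and different power.

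Two things are at stake. If the rule stays open, whichever half succeeds can be chosen after the data are seen. And a non-significant histology comparison could be reported as CTG and ADM being alike, with 0.90 power cited in support, when nothing in the plan ties that figure to histology. Histology is the first core objective in Section 1 and the first-listed outcome, so this matters to the trial's main message.

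**Working it through.** **Inputs from Section 7.** Two-sided alpha 0.05; unequal-variance (Welch) t-test; 22 per group; power 0.90; 60 enrolled with 6 lost. Section 3 gives three groups. Equal allocation is implied by 22 in each group, so 60/3 = 20 per group enrolled and (60 − 6)/3 = 18 per group after losses.

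**1. The plan's own figure.** It cannot be reproduced directly, because no difference or SD is stated. Solving backwards with the normal approximation, d = (1.960 + 1.282) × √(2/22) = 0.977. With the noncentral t (equal SDs), d = 1.0005. So 22 per group with 0.90 power corresponds to a difference of about 1 SD in one continuous variable. At d = 1 the t-test power is:

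| Per group | Power |
|---|---|
| 22 | 0.90 |
| 20 | 0.87 |
| 18 | 0.83 |

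**2. Reading A: either part is enough to reject.** Each part is tested at 0.05. If independent, type I error = 1 − (1 − 0.05)² = 0.0975. For two-sided tests on bivariate normal statistics, it is 0.091 at correlation 0.5 and 0.078 at correlation 0.8. The documents give no correlation, so this is a range: about 0.08 to 0.10, not 0.05.

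**3. Reading B: both parts are needed.** Joint power cannot exceed the smaller of the two powers. If each part had 0.90, joint power is 0.90 × 0.90 = 0.81 at correlation 0, 0.83 at 0.5 and 0.86 at 0.8. That is below the stated 0.90.

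Over this range of correlation, and with 0.90 power for each part, Reading A loses the 0.05 and Reading B loses the 0.90.

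**4. What 0.90 could mean for histology alone.** The scale is not stated, so these are assumptions, all at 22 per group and two-sided 0.05.

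If histology is a numeric score (t-test):

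| Difference | Power |
|---|---|
| 0.5 SD | 0.37 |
| 0.8 SD | 0.74 |
| 1.0 SD | 0.90 |
| 1.2 SD | 0.97 |

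If histology is a yes/no finding (exact enumeration of two binomials):

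| Rates | Welch, as planned | Fisher's exact |
|---|---|---|
| 50% v 80% | 0.55 | 0.43 |
| 40% v 80% | 0.79 | 0.69 |
| 40% v 90% | 0.96 | 0.93 |

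At 18 per group, Welch gives 0.50 for 50% v 80% and 0.74 for 40% v 80%.

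Power for histology therefore runs from well below 0.90 to above it, depending on inputs that the plan does not supply.

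**The case against.** A reader might infer that the 0.90 power is simply false for histology. The documents do not show that. A numeric score differing by about 1 SD, or a yes/no finding at 40% v 90%, would reach 0.90 at 22 per group.

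Nor is it settled that histology is yes/no. The protocol title speaks of histomorphometric outcomes, Section 2 names the percentage of vital bone as the histologic outcome, and Section 7 speaks of equal means. All three suggest a measured quantity, for which a Welch test is ordinary. Even on yes/no data the planned test is serviceable: its type I error at 22 per group was 0.043 to 0.051 for rates of 10% to 90%. Judging the plan by Fisher's exact test makes the shortfall look 0.10 to 0.12 larger in the 50% v 80% and 40% v 80% cases than under the test it actually names.

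A reader might also infer that 0.90 is sound for thickness. That is not supported either. No difference or SD is stated for thickness, and 60 enrolled is fewer than the 66 that the power sentence requires.

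Finally, a type I error of 0.10 is the upper end of the range under Reading A, since both parts come from the same patient and site and may be positively correlated.

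These arguments stand, and they limit the point to what is not defined and not established. They do not supply the missing decision rule or histology scale, and nothing elsewhere in the document does.

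**Conclusion.** The point holds in this form. The joint null carries an alpha and a power that do not fit it together: type I error is about 0.08 to 0.10 if either part suffices, or joint power is about 0.81 to 0.86 if both are needed and each has 0.90. This assumes each part is tested at 0.05 and that the correlation between them lies between 0 and 0.8.

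For histology alone, 0.90 is not established rather than shown to be wrong. The yes/no figures rest on an assumed scale and assumed rates. For thickness, the sample size is consistent with a 1 SD difference that the plan does not state, and at the numbers actually planned the power for that difference would be 0.87 or 0.83.

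**What to change.** In Section 7:

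- Limit the null, the 0.05 alpha and the power statement to one named endpoint. Vertical soft tissue thickness in mm fits the stated test. The investigator should confirm the choice, because histology is currently listed first among the objectives and outcomes.
- State the difference and SD assumed for that endpoint, and restate power for the number actually enrolled. If the intended difference is 1 SD, that is 0.87 at 20 per group and 0.83 at 18 per group. Reconcile the 66 required with the 60 to be enrolled.
- Define how attachment and keratinization are scored before any slide is read. Analyse them separately with a test that matches the scale: Fisher's exact if yes/no, rank-sum if graded, Welch if a numeric measurement. Report an estimate of the difference with a 95% CI, and claim no power.

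This is a text change that needs no new data. The price is a power claim that is narrower in scope and slightly lower, and an explicit decision about which outcome leads.

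### The allowance for losses lowers enrolment instead of raising it, so 60 patients cannot supply the 22 per group that the stated 0.90 power requires

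*Combined protocol and SAP*

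**What the plan says.** Section 7 (Data Analysis/Outcome measures) contains the whole sample-size justification. The hypothesis is a comparison of the two graft materials: "The null hypothesis is CTG and ADM materials will have the same soft tissue thickness". The test is specified as having a "significance level (alpha) of 0.05 using a two-sided two-sample unequal-variance t-test". The requirement and the enrolment follow in consecutive sentences: "22 patients in each group (total of 66) will reach 0.90 statistical power. Accounting for a 6-patient loss-to-follow up, 60 patients will be enrolled".

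Section 3 (Study Population, Protocol Procedure, and Method) gives the same enrolment figure, "Approximately 60 adults determined to need ridge augmentation graft", and three arms: "Patients will be randomized like the flip of a coin to one of the three groups listed". The arms are connective tissue graft (CTG), acellular dermal matrix (ADM) and a control without soft tissue augmentation. No unequal allocation ratio is given, and 22 in each of three groups making 66 implies 1:1:1.

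Neither section gives the mean difference or the SD behind the 0.90.

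**The concern.** The two sentences in Section 7 cannot both hold. If 66 patients are needed for 0.90 power and 6 may be lost, enrolment has to exceed 66. The plan enrols fewer than 66, so it falls short of its own requirement before anyone is lost.

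The power claim matters most if CTG and ADM do not differ significantly. A reader who trusts the protocol would take the chance of missing the planned difference to be 10%. With the enrolment and losses the plan itself expects, that chance is higher, and a null result would be given more weight than it deserves.

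**Working it through.** **Inputs.** From Section 7: two-sided alpha 0.05, two-sample t-test, 22 per group, total 66, power 0.90, 6 losses, 60 enrolled. From Section 3: three groups, about 60 enrolled. Not given: mean difference, SD, and how the losses divide between arms.

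**1. Head count.**
- Stated total: 3 × 22 = 66. This reproduces.
- Stated enrolment: 66 − 6 = 60. Only subtraction gives this figure.
- Losses added: 66 + 6 = 72, or 24 per group.
- Losses as a proportion, N / (1 − loss rate): 66 / (1 − 6/66) = 72.6, so 73. At 10% loss, 66 / 0.90 = 73.3, so 74. No form of inflation gives 60.
- What 60 provides: 60 / 3 = 20 per group with no loss; (60 − 6) / 3 = 18 per group if losses are even.

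**2. Effect implied by 22 per group.** Because no difference or SD is stated, the 0.90 cannot be reproduced directly. It can be solved backwards. With n per group and standardised difference d, the t statistic has 2n − 2 degrees of freedom and noncentrality d × √(n/2). Power is the probability that this noncentral t exceeds the 97.5% point of the central t (the opposite tail is negligible). Setting power to 0.90 at n = 22 (42 df, critical value 2.018) gives d = 1.0005, about 1.0 SD.

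**3. Power at the numbers the plan will have, with d held at 1.0005.**

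| Per group | Noncentrality | Critical t | Power | Difference detectable with 0.90 power |
|---|---|---|---|---|
| 22 | 3.318 | 2.018 | 0.900 | 1.00 SD |
| 20 (60 enrolled, no loss) | 3.164 | 2.024 | 0.869 | 1.05 SD |
| 18 (60 enrolled, 6 lost evenly) | 3.002 | 2.032 | 0.830 | 1.11 SD |

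Type II error at 18 per group is 1 − 0.830 = 0.170, against the planned 0.10.

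**4. Sensitivity.**
- *Normal approximation:* implied d = 0.977; power 0.871 at 20 and 0.834 at 18.
- *Unequal variances, lowest possible Welch df (n − 1):* implied d = 1.025; power 0.868 at 20 and 0.826 at 18. Simulating the Welch test with SD ratios of 1, 1.5 and 2 also gives about 0.83 at 18.
- *22 reached by rounding up:* d can be at most the value giving 0.90 at 21 per group, which is 1.025. Power is then 0.885 at 20 and 0.848 at 18.
- *Uneven losses from 20/20/20 at d = 1.0005:* all six in the control arm leaves CTG versus ADM at 20 v 20, power 0.87; all six in one graft arm leaves 20 v 14, power about 0.80.

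Power stays below 0.90 in every case.

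**The case against.** The strongest counter-argument is that the labels may have been swapped: 66 enrolled, 6 lost, 60 completing, with 20 per group as the powered number. The arithmetic is consistent with that, and the implied difference would then be about 1.05 SD. But the text attaches 0.90 to 22 per group, and Sections 3 and 7 both give 60 as the enrolment. If a swap was intended, both sections are wrong and still need correcting. What stands is that the documents show a conflict without showing which figure the sponsor meant, so the sponsor has to settle that.

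The power figures can also fairly be called conditional. They rest on an effect the documents never state and on an even division of losses that the plan does not promise. The coin-flip description of randomisation mentions no blocking, so even 20/20/20 is not assured. Losses in the control arm would not affect the CTG versus ADM test at all. All of this is correct, and it is why 0.83 should be read with the range of about 0.80 to 0.87 for different patterns of loss, and 0.85 if 22 was rounded up. It does not touch the head count: for any fixed difference that gives 0.90 at 22 per group, 20 or 18 per group gives less.

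Finally, the drop is moderate, about 3 points with no loss and 7 with six even losses. The trial remains informative; the fault is in the power claim.

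**Conclusion.** The concern holds. Planned enrolment of 60 is below the 66 that the same paragraph requires, and the loss allowance widens the gap instead of covering it. This follows from the plan's own figures and needs only the equal allocation implied by 22 in each of three groups.

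The size is conditional. Taking the difference implied by 22 per group (about 1.0 SD) and even losses, power is about 0.83, not 0.90, and type II error about 17%, not 10%. With no losses, power is about 0.87. The wording must be corrected because 0.90 is the only performance claim made for the sample size and the stated enrolment cannot deliver it.

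**What to change.** First establish which of 22, 66 and 60 is the wrong figure, and state the assumed mean difference in mm and the SD that produced the calculation. Then correct Section 7 and bring Section 3 into line, in one of these ways:

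- **Keep 60 enrolled and restate the power.** For example: *60 patients (20 per group) will be enrolled. If 6 are lost evenly (18 per group), the two-sided t-test has about 0.83 power for a difference of 1.0 SD, or 0.90 power for 1.11 SD.* The SD values here are back-solved and illustrative; replace them, and the power, with results from the sponsor's own difference and SD.
- **Keep 0.90 power by numbers alone.** Enrol 72 (24 per group), leaving 22 per group after 6 even losses. This adds 12 patients.
- **If the totals were swapped.** State that 66 will be enrolled and 60 are expected to complete, and tie 0.90 to 20 per group (a difference of about 1.05 SD). This adds 6 patients to the present enrolment figure.

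The first option costs one paragraph and a less favourable power figure, with no extra patients.
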